#### Assessing the patient's current self-management strategies for self-care

The Clinical Investigator will assess each participant's self-care regime and make recommendations. They will make the following mindfulness, sleep, and movement recommendations listed below.

**Practice mindfulness:** Have some quiet time to yourself once a day. Listen to a guided meditation or grab a journal. Write down your thoughts. Let go of stress and try to relax. Try chanting, prayer, or using a mantra.

#### **Protocol**

Study Title: Integrative Medicine for Hypermobility Spectrum Disorder (HSD) and Ehlers-Danlos (EDS) syndromes: A mixed-methods feasibility study (IMforHSDandEDS)

PI: [name]

IRB #: DH10320/PRAF

Approval Date: 03.03.21

Version: 3.0

**Mindful eating:** Take some time to slow down and eat your food. This will help you tune in with your body. It might take time to listen to your body's natural satiety cues to know when you are hungry or full at first. Try cooking, meal-prepping, and eating with others. Incorporate their support with the food plan to help you keep on track.

Try to focus on having non-distracted eating during meals. This means silencing your cellphone, turning off your TV or computer, and savoring your food.

Mindful eating	
Eat/drink with intention
 
 
• How did the food make you feel?
 
• Are you enjoying it?
 
 
Listen to your hunger/thirst
 
 
• Is your stomach growling?
 
• Are you parched?
 
 
Slow down
 
 
• Slow down for a moment and enjoy your food. This will help you listen to your hunger and get pleasure out of eating. Take your time.
 

----------------	--

**Sleep:** Try to sleep 7-8 hours at night. Practice good sleep hygiene by having a wind-down time at night without electronics (at least 2 hours before bedtime). Avoid eating a heavy meal or drinking alcohol before bed.

**Movement (light physical activity):** Try to take your lunch break outside or go on a walk after work. It might take some time to build up the energy, so start slowly, maybe 15 minutes a day at first.

#### Assessing the patient's current self-management strategies for mental health

The Clinical Investigator will determine the mental health needs of participants and make mental health provider referrals as needed. If additional support is required and a referral is made, the Clinical Investigator will revisit these needs and check on progress in follow-up visits.

Patients will also be referred to mental health resources found at the Ehlers-Danlos Society website.

#### **E.6 Measures**

##### Primary Outcome measures:

##### *Feasibility*

- Retention rate (proportions of participants completing 5 and 9-week visits)

##### **Protocol**

Study Title: Integrative Medicine for Hypermobility Spectrum Disorder (HSD) and Ehlers-Danlos (EDS) syndromes: A mixed-methods feasibility study (IMforHSDandEDS)

PI: [name]

IRB #: DH10320/PRAF

Approval Date: 03.03.21

Version: 3.0

- Recruitment rate (average number of participants enrolled per month)
- Dropout rate (proportions of participants failing to complete 5 or 9-week visits)

### Secondary Outcome measures:

#### *Dietary Adherence/Food Tracking Feasibility (MyFitnessPal food tracking):*

- Dietary adherence will be measured by self-reported food tracking through Daily Nutrition Goals in the *MyFitnessPal* app and will be documented at 5 and 9 weeks through the Friends feature. Daily macronutrient contributions will be obtained as percentages of total intake. The suggested macronutrient breakdown for the food plan is 40-50% calories from a carbohydrate source, 35-40 % calories from fat, and 15-20% calories from protein. Weekly recorded consumption of the participant will be compared to this standard for an adherence score. For each of the three macronutrient categories, we will give 2 points if the percentage is within the required range and 1 point if the percentage is within 5% of the required range (maximum 6 points total). A score of 4 and above will be considered adherent to the food plan.
- The feasibility of food tracking will be measured by adherence to the recommended use of the app. A threshold of 3 days of reporting per week (including breakfast, lunch, dinner, and snacks) for the 9-week duration of the study will be considered adherent and should provide sufficient data to assess the observance of the recommended food tracking.

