#### *Prescribing an anti-inflammatory food plan and assessment of current diet*

The Clinical Investigator will prescribe an anti-inflammatory food plan that consists of a high intake of fruits and vegetables (4-5 serving of each per day). The specific dietary requirements for adherence to the anti-inflammatory food plan incorporated in this 9-week integrative medicine intervention will include macronutrient levels similar to those of a Mediterranean diet, which breaks down to 40-50% carbohydrates, 15-20% protein, and 35-40 % fat. Such a diet is high in fiber, micronutrients, healthy fats, and antioxidants that may provide health benefits by reducing inflammation. The Clinical Investigator will present the macronutrient requirements, assess the current diet of the participant, and suggest modifications that will cause their diet to conform to study guidelines, such as reducing sugar as well as processed and fast foods. They will discuss removing trans fats and hydrogenated oils and replacing them with cold-pressed and unrefined oils. For simplicity and accuracy, participants will be advised to follow a "Mediterranean-style eating pattern," which is very searchable among recipe databases and websites, and more specific than the term "anti-inflammatory."

Participants will be provided an anti-inflammatory food plan that includes recipes, a guide for adding and reducing certain foods, and obtaining targeted macronutrient levels (see above) if modification of their current diet seems infeasible, or if they so desire. The student researcher will assess the cooking skills of participants and provide resources, as needed (i.e. YouTube channels, websites). They will discuss meal-planning, meal-prepping, and making a grocery list on a budget as needed. Additionally, participants will be contacted twice via phone or email by the student researcher to provide nutritional and psychosocial support, answer any questions, and facilitate adherence.

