#### MyFitnessPal

#### **Protocol**

Study Title: Integrative Medicine for Hypermobility Spectrum Disorder (HSD) and Ehlers-Danlos (EDS) syndromes: A mixed-methods feasibility study (IMforHSDandEDS)

PI: [name]

IRB #: DH10320/PRAF

Approval Date: 03.03.21

Version: 3.0

*MyFitnessPal*, a food tracker available on both Apple and Android for mobile devices, as well as both Windows and Mac computer platforms, will be used to collect estimated daily dietary intake for participants. *MyFitnessPal* has a database of nutritional information for over 11 million foods that will allow participants to capture their general diet by manually adding individual ingredients, barcode scanning, or finding whole meals. In a comparison of micronutrients and calories between diet-tracking apps and the USDA database, *MyFitnessPal* was shown to have the best coding accuracy. Self-reported data, however, may be subject to inaccuracies. When foods are entered into the *Diary* feature located in the app, the *Nutrient Dashboard* displays daily calories, as well as macronutrient proportions, broken down into carbohydrates, fats, and protein.

Participants will be encouraged to track their daily diet to the best of their ability, and for weeks that there is missing data, a threshold of no less than 3 days of tracking (including breakfast, lunch, dinner, and snacks) per week for the 9-week study duration will be considered adherent and averaged appropriately. Individuals with previous disordered eating patterns, or discomfort with food tracking, will be able to opt-out; however, they will still be shown how to use *MyFitnessPal* to analyze dietary composition for adherence. A 1-week lead-in prior to introducing the food plan will be utilized to provide a baseline record of the participant's general diet. *MyFitnessPal* data will allow us to track general adherence to dietary changes, the overall quality of the participant's diet, and average macronutrient proportions. By measuring the participant's reported macronutrient percentage scores and comparing them with the prescribed food plan, we will be able to calculate an adherence score.

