### **E.9 Statistical Analysis**

All measures collected in the study, including baseline characteristics and outcome measures, will be summarized using mean and SD (biomarkers, anthropometrics), median and IQR (Beighton score), or percentage within each level, for categorical variables. All statistical analyses will be performed at the National University of Natural Medicine.

For Specific Aim 1,

Feasibility of the 9-week integrative medicine intervention will be measured through recruitment and retention at each follow-up visit. Recruitment rate will be presented as the mean number of participants enrolled per month, with enrolment ceasing either after 4 months, or when n=20 participants have been enrolled. Retention will be calculated as the percentage of enrolled participants from whom follow-up data is obtained, at either the 5-week or 9-week visit.

For Specific Aim 2,

Adherence to the recommended diet will be assessed in different ways and tracked by macronutrient levels and dietary composition. In particular, we will assess:

- Percentage of days on which the diet recommendations were met; in order to satisfy this requirement, macronutrient distribution must meet all of the following:
  - Carbohydrates between 40-50%
  - Protein between 15-20%
  - Fat between 25-30 %
- Number of weeks in which recommendations were met at least 5 days;
- Whether recommendations were met on at least 75% of total days (Y/N)
- Mean of weekly adherence scores calculated over the 9-week study period.

Percentage of days and weeks adherent will be summarized across participants as median/IQR/range. We will also present the percentage of participants who met the threshold of 75% days adherent.

Feasibility of the 9-week integrative medicine intervention will also be measured through self-reported food plan satisfaction surveys that assess any negative outcomes, overall cost-prohibitiveness or

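### The weekly food-plan adherence score measures conformity to macronutrient targets, not adoption of the prescribed plan, and it is not referenced to the lead-in diet

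*Combined protocol and SAP*

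**What the plan says.** **The score.** E.6 (Secondary Outcome measures) compares each week's recorded intake with "40-50% calories from a carbohydrate source, 35-40 % calories from fat, and 15-20% calories from protein". Each macronutrient earns two points when its share lies inside the stated limits. For a near miss it earns "1 point if the percentage is within 5% of the required range (maximum 6 points total". The cut-off follows: "A score of 4 and above will be considered adherent to the food plan". For this score, E.9 (Specific Aim 2) lists one summary: "Mean of weekly adherence scores calculated over the 9-week study period". The other three diet-adherence measures in E.9 count days or weeks on which all three macronutrient ranges are met.

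**The plan being adhered to.** E.5 (Prescribing an anti-inflammatory food plan) describes a plan that "consists of a high intake of fruits and vegetables (4-5 serving of each per day". It also describes suggested modifications "such as reducing sugar as well as processed and fast foods" and a change of fats and oils. The same paragraph names macronutrient levels among the requirements for adherence.

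**The lead-in.** E.5 (MyFitnessPal) states: "A 1-week lead-in prior to introducing the food plan will be utilized to provide a baseline record". Its stated analytic use is in Exploratory Aim 1 (B.4). No adherence measure in E.6 or E.9 refers to it.

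**Fat range.** E.4.4, E.5 and E.6 give 35-40%. E.8 and the daily criterion in E.9 give 25-30%.

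**The concern.** The outcome label claims more than the rule measures. Two diets with the same macronutrient split score the same whatever foods supply it, so the score cannot show whether the prescribed foods were eaten. Without the lead-in week as a reference, it also cannot separate a participant who moved to the targets from one who was already there.

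The protocol itself suggests a wider measure. E.5 says the app data will track overall diet quality, and E.9 opens by naming dietary composition beside macronutrient levels. Neither is given an adherence measure.

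Section F says the methods could be carried into a larger study. A good weekly score might then be read as evidence that patients can adopt the plan, when it shows only that their reported macronutrient split lay near the targets.

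**Working it through.** **1. Reproduce the plan's own figure.** Three macronutrients × 2 points = 6, the stated maximum. With the E.6 ranges it is attainable: of the 5,151 whole-percent splits that sum to 100, 36 score 6.

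**2. Apply the rule to example diets** (carbohydrate/protein/fat, E.6 ranges). E.6 does not say whether the tolerance of 5% is in percentage points or relative to the limits, so both are shown.

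| Split | Percentage points | Relative 5% |
|---|---|---|
| 50/15/35 | 2+2+2 = 6 | 2+2+2 = 6 |
| 48/16/36 | 2+2+2 = 6 | 2+2+2 = 6 |
| 55/15/30 | 1+2+1 = 4 | 0+2+0 = 2 |
| 56/15/29 | 0+2+0 = 2 | 0+2+0 = 2 |

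Under the percentage-point reading, 55/15/30 is adherent with two of its three components outside the range. The number of whole-percent splits scoring 4 or more is 206 with percentage points and 102 with the relative reading. No food enters either calculation.

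**3. No change against full change.** A participant at 50/15/35 in the lead-in and in every later week scores 6 throughout: change = 6 − 6 = 0, every week labelled adherent. A participant who moves from 56/15/29 to 50/15/35 goes from 2 to 6: change = 4. The on-plan scores of the two are identical, and only the lead-in score separates them.

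**4. How often could an unchanged diet pass?** The documents give no usual intakes, so this is illustration only. Assumptions: weekly carbohydrate is normal with SD 3, 5 or 8 points, protein has half that SD, and fat is the remainder. The table shows the share of unchanged weeks scoring 4 or more across the three SDs.

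| Assumed usual mean | Percentage points | Relative 5% |
|---|---|---|
| 48/16/36 | 48-92% | 28-74% |
| 55/15/30 | 23-30% | 7-15% |
| 58/14/28 | 4-19% | 1-9% |

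The answer depends mainly on where participants start, which the lead-in week would show.

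**5. The daily criterion in E.9.** It requires carbohydrate 40-50, protein 15-20 and fat 25-30 on the same day. The upper limits sum to 50 + 20 + 30 = 100, so only exactly 50/20/30 passes when the three shares sum to 100. A day at 50/15/35, which scores 6 under E.6, fails it. The choice of fat range also changes the weekly score: with 25-30%, 50/15/35 scores 5 (percentage points) or 4 (relative) instead of 6.

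**6. Does the lead-in fall inside the nine-week mean?** E.4.1 sets the visits at 5 and 9 weeks after enrolment, and E.4.4 places the lead-in after Visit 1. The pre-plan week may therefore be one of the nine weeks averaged; the text does not say. If it is, each point of lead-in score moves the mean by 1/9 = 0.11, and by at most 6/9 = 0.67.

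**The case against.** The strongest reply is that the protocol chose a macronutrient definition openly. E.5 lists macronutrient levels among the requirements for adherence, B.2 repeats the comparison, and E.4.5 and E.4.7 say the general healthy-eating script used at check-ins does not count towards food-plan adherence. This stands in part: scoring macronutrients is a legitimate choice. It does not justify the wider label, because the same part of E.5 prescribes foods that the score never sees.

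A second reply is that adherence ordinarily means meeting a target, not moving towards it. That is right, and someone already at target should not be marked down. The lead-in score should stand beside the on-plan score, not redefine it.

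A reader might infer three stronger claims, and the documents support none of them:

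- *Aim 2 goes unanswered.* Aim 2 also covers food-plan feasibility, through the satisfaction survey, and tracking feasibility, through days logged. Neither uses this score.
- *Every adherence measure would be falsely favourable.* The day-based measures in E.9, as printed, would read near zero, because almost no day can pass. E.9 also does not list the proportion scoring 4 or more; for the score it lists only the mean.
- *The study cannot detect an unchanged diet at all.* For Exploratory Aim 1, E.9 computes changes in each measure from baseline to 5 and 9 weeks, dietary composition included. The missing reference concerns the adherence measures only.

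**Conclusion.** The point holds for the weekly score in E.6 and its mean in E.9. They measure conformity to macronutrient targets. They do not show that the prescribed foods were eaten, or that anyone changed diet. An unchanged 50/15/35 diet scores 6 of 6 under either reading of the tolerance. This follows from the rule alone and needs no assumption about usual intake.

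The frequency of such cases is unknown. The range of about 4% to 92% (percentage points) or 1% to 74% (relative) rests wholly on assumed usual diets and spreads, and it should not be read as a prediction that the study will report false adherence.

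The consequence is confined to the adherence part of a secondary, descriptive aim in at most 20 participants. It is still worth correcting, because the correction is nearly free and decides what the adherence result can be said to show.

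**What to change.** In E.6 and E.9:

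1. Score the lead-in week by the same rule and exclude it from the on-plan mean. State how many on-plan weeks that mean then covers.
2. Report for each participant the lead-in score, the mean on-plan score and the change, with the percentage scoring 4 or more in each period. Keep *adherent* as meeting the target.
3. Rename the outcome *adherence to macronutrient targets*. Optionally, add a descriptive food-content measure from the diaries, with its coding rule fixed before the data are seen; the protocol has no such rule now.
4. State whether the 5% tolerance is in percentage points or relative.
5. Reconcile the fat range between E.4.4, E.5 and E.6 (35-40%) and E.8 and E.9 (25-30%), and then check that the daily criterion can be met by more than one split. Which range is intended is for the investigators to say.

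Items 1 to 5 need no new data. The cost is wording, one extra score per participant and, if the optional measure is chosen, diary coding for at most 20 people. The adherence result may look less favourable.

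### The 0–6 dietary adherence score with a cut-off of 4 can fail a week close to the food plan and pass one further away; report distance outside the ranges beside it

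*Combined protocol and SAP*

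**What the plan says.** Section E.6 (Measures, Secondary Outcome measures) sets the standard as "40-50% calories from a carbohydrate source, 35-40 % calories from fat, and 15-20% calories from protein". On the scale it says: "Daily macronutrient contributions will be obtained as percentages of total intake". On the unit scored it says: "Weekly recorded consumption of the participant will be compared to this standard for an adherence score". For each macronutrient the rule is to "give 2 points if the percentage is within the required range and 1 point if the percentage is within 5% of the required range". Anything further out implicitly gets 0. The section gives the ceiling as "maximum 6 points total". The verdict is: "A score of 4 and above will be considered adherent to the food plan".

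Section E.9 (Statistical Analysis, Specific Aim 2) lists four summaries of dietary adherence. Three count days or weeks on which all three macronutrients were in range. The fourth is the "Mean of weekly adherence scores calculated over the 9-week study period". E.9 does not repeat the cut-off of 4, and its fat range is 25–30% where E.6 has 35–40%.

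**The concern.** A graded score is there to give partial credit to near misses, so one expects a week nearer the prescribed ranges to do at least as well as one further away. Here it may not. The three shares come from one total, so when carbohydrate rises, protein and fat must fall between them by the same amount. If a participant eats near a corner of the permitted region, a small shift puts all three shares just outside at once and costs three points. A much larger swap between only two macronutrients costs two.

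Adherence to the food plan is the study's Secondary Aim (B.2). At stake are the E.6 weekly verdict and the mean weekly score in E.9, for diets close to the plan.

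**Working it through.** **Inputs, all from E.6.** Ranges: carbohydrate 40–50, protein 15–20, fat 35–40. Points: 2 in range, 1 within 5 of the range, otherwise 0. Cut-off: 4. Splits are written carbohydrate/protein/fat.

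**Assumptions.** The tolerance means percentage points, limits included, which E.6 does not say. The three shares sum to 100, so energy from alcohol is outside the denominator.

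**The plan's own figure.** Three macronutrients × 2 points = 6, as stated.

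**Step 1: what the cut-off means.** Take two macronutrients in range and find the third by subtraction.
- Protein and fat in range: they total 50 to 60, so carbohydrate is 40 to 50, in range.
- Carbohydrate and protein in range: they total 55 to 70, so fat is 30 to 45, at most 5 out.
- Carbohydrate and fat in range: they total 75 to 90, so protein is 10 to 25, at most 5 out.

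So 2+2+0 cannot occur. The only passing patterns are 2+1+1, 2+2+1 and 2+2+2. A score of 4 or more therefore means that nothing is more than 5 points out and at least one macronutrient is inside.

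**Step 2: the misordered pair.** Departure = distance to the nearest range limit, or 0 if inside.

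| Split | Departures | Largest | Total | Score | Verdict |
|---|---|---|---|---|---|
| 52/14/34 | 2, 1, 1 | 2 | 4 | 1+1+1 = 3 | fails |
| 55/10/35 | 5, 5, 0 | 5 | 10 | 1+1+2 = 4 | passes |

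The order is reversed on both measures of distance. In E.9's mean the nearer week contributes 3 and the further week 4.

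**Step 3: why it happens at the corners.** 50 + 15 + 35 = 100 and 40 + 20 + 40 = 100, so both corners meet the plan exactly and score 6. Moving from 50/15/35 to 50.5/14.75/34.75 gives departures 0.5 + 0.25 + 0.25 = 1.0, a score of 3, and a fail.

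**Step 4: how much is affected.** All whole-percent splits summing to 100 with nothing more than 5 points out:
- 2+2+2: 36
- 2+2+1: 60
- 2+1+1: 110
- 1+1+1: 20

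The first three patterns pass: 36 + 60 + 110 = 206. The last fails. The total is 206 + 20 = 226. Of the 20 that fail, 12 are strictly nearer than the worst accepted week (total below 10, largest below 5) and 8 tie with it (total 10, largest 5).

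**Step 5: other readings (whole percents, total departure).**

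| Reading | Worst passing week | Best failing week |
|---|---|---|
| 5 points inclusive, fat 35–40 | 10 | 4 |
| 5 points strict, fat 35–40 | 8 | 4 |
| 5% relative, fat 35–40 | 5 | 2 |
| 5 points inclusive, fat 25–30 | 15 | 7 |

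The figures move but the reversal remains. Step 1 holds only for the E.6 fat range. With 25–30, 40/15/45 scores 2+2+0 = 4 and passes with fat 15 points out.

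**The case against.** The strongest reply is that the rule does not contradict itself. Moving any one macronutrient closer to its range never lowers its points, so a week at least as good on all three never scores lower. 52/14/34 and 55/10/35 are not ordered in that sense, because the second is better on fat. The reversal appears only once a distance is chosen, and E.6 defines adherence by ranges met or nearly met. This stands as far as it goes. The answer is that the reversal occurs on both obvious distances, the total and the largest departure.

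A reader might infer four stronger things, none of which the documents support.
- **That the sum to 100 is the whole cause.** Any banded score can misorder weeks by distance. The sum adds the corner effect.
- **That a reported adherence percentage will be wrong.** The only participant percentage E.9 specifies for diet is the share reaching 75% of days with all three in range. No test or go/no-go decision uses the cut-off of 4.
- **That most near-plan weeks are misclassified.** The 20 of 226 is a count of possible splits. Nothing in the documents says how often participants would fall there.
- **That relaxing the yes/no rule cures the problem.** On total distance it does not. Of the 48 failing whole-percent splits less than 10 points out in total, only 12 are 1+1+1. The other 36 fail because one macronutrient is more than 5 out, and they would still fail.

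**Conclusion.** The concern holds, with modest effect. As written, the score can call a week nearer the plan non-adherent and a week further away adherent: largest departure 2 against 5, total 4 against 10. The exact figures rest on the E.6 fat range, a tolerance of 5 percentage points inclusive, and shares that sum to 100. The reversal itself survives the strict and relative readings and the E.9 fat range.

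The consequence is confined to the weekly verdict in E.6 and to one of four descriptive summaries in E.9, for a secondary aim in a single-arm feasibility study of up to 20 people. The all-in-range day counts in E.9 are unaffected, but they give no credit for near misses and so cannot stand in for a graded measure. This is worth correcting because the correction is cheap. It does not threaten the study's primary conclusions.

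**What to change.** 1. **E.9, main change.** Beside the mean 0–6 score, report the weekly distance outside the three ranges in percentage points, as the total and as the largest single departure, averaged over scored weeks. On each measure a nearer week then always has a better value.
2. **E.6, if the yes/no verdict is kept.** Base it on the largest departure: no macronutrient more than 5 percentage points outside its range. With the E.6 ranges this keeps all 206 whole-percent splits that now pass, adds the 20 that score 1+1+1, and removes the reversal on that measure. State that it is slightly more lenient and does not order weeks by total distance: 39/15/46 (departures 1 + 0 + 6 = 7) still fails while 55/10/35 (total 10) passes.
3. **E.6, wording.** Say whether the 5% tolerance is in percentage points, whether the limits are included, and whether energy from alcohol counts in the denominator.
4. **Before computing anything.** Reconcile the fat ranges in E.6 and E.9, since every measure above depends on which applies.

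The cost is a few sentences in E.6 and E.9. The same recorded intake is used and no new data are needed.
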